## 12. SAFETY EVALUATION

## **12.1 EXTENT OF EXPOSURE**

On Day 6, subjects were on fast for 10.00 hours prior to dose administration and for 4.00 hours post dose in each study period. Subjects were administered a single dose of either Treatment A or Treatment B as per randomization scheme with about 240 mL of water for the subjects who were assigned A; 120 mL for LANOXIN® (digoxin) USP 250 mcg and 120 mL for Spironolactone Oral Suspension 100 mg (Carospir® Oral Suspension 20 mL of 25 mg / 5 mL) for the subjects who were assigned B, at ambient temperature in sitting position in each study period. Oral cavity check was done immediately after drug administration to assess the compliance to this procedure.

Total 28 subjects had completed the clinical phase of the study successfully. Plasma and urine samples of 28 subjects were analyzed and plasma and urine concentration data of all 28 subjects was considered to draw statistical conclusion.

The duration of clinical phase was 39 days, including the washout period of 28 days between each study period.

### 12.2 ADVERSE EVENTS (AEs)

## 12.2.1 Brief summary of adverse events

There were no adverse events reported in this study.

#### 12.2.2 Display of adverse events

There were no adverse events reported in this study.

#### 12.2.3 Analysis of Adverse Events

There were no adverse events reported in this study.

#### 12.2.4 Listing of Adverse Events by Subject

There were no adverse events reported in this study.

# 12.3 DEATHS, OTHER SERIOUS ADVERSE EVENTS, AND OTHER SIGNIFICANT ADVERSE EVENTS

There were no deaths or serious adverse events reported in this study.

# 12.3.1 Listing of Deaths, other Serious Adverse Events and Other Significant Adverse Events

Not applicable

#### 12.3.1.1 Deaths

Not applicable

Protocol No. C-CMP-SPI-001

Confidential

Page 51 of 64

#### (Fasting Condition)

Confidential

## 12.3.1.2 Other Serious Adverse Events

Not applicable

## 12.3.1.3 Other Significant Adverse Events

Not applicable

## 12.3.2 Narratives of Deaths, Other Serious Adverse Events and Certain Other Significant Adverse Events

Not applicable

### 12.3.3 Analysis and Discussion of Deaths, Other Serious Adverse Events and Other Significant Adverse Events

Not applicable

#### 12.4 CLINICAL LABORATORY EVALUATION

#### 12.4.1 Listing of Individual Laboratory Measurements by Subject

The individual laboratory measurements of each subject were given in Appendix 16.2.8.

#### 12.4.2 Evaluation of Laboratory Parameter

#### 12.4.2.1 Laboratory Values over Time

The screening clinical laboratory investigations included hematology, serum biochemistry, serology and urine analysis as detailed in the protocol. The hematology (except blood grouping and Rh typing) and biochemistry (except random blood sugar) investigations done at screening were repeated at the end of the study.

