#### Table 9: Subject disposition (All Subjects)

	Sequence 1	Sequence 2	All
	AB	BA	Subjects
Subjects			
Randomized	14	14	28
Completed	14	14	28
Discontinued	00	00	00

Treatment A: LANOXIN® (digoxin) USP 250 mcg (substrate drug)

Treatment B: LANOXIN® (digoxin) USP 250 mcg + Spironolactone Oral Suspension 100 mg (Carospir® Oral Suspension 20 mL of 25 mg / 5 mL)

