#### 12.4.2.2 Individual Subject Change

Not applicable

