### Electrolyte and Metabolic Abnormalities

In addition to causing hyperkalemia, Spironolactone Oral Suspension can cause hyponatremia, hypomagnesemia, hypocalcemia, hypochloremic alkalosis, and hyperglycemia. Asymptomatic hyperuricemia can occur and rarely gout is precipitated. Monitor serum electrolytes, uric acid and blood glucose periodically. *Gynecomastia* 

Spironolactone Oral Suspension can cause gynecomastia. In RALES, patients with heart failure treated with a mean dose of 26 mg of spironolactone once daily, about 9% of the male subjects developed gynecomastia. The risk of gynecomastia increases in a dose-dependent manner with an onset that varies widely from 1-2 months to over a year. Gynecomastia is usually reversible.

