### 4.2 Randomization

The order of receiving the treatment A and treatment B for each subject during the study will be determined randomly. According to the randomization schedule, subjects will receive the assigned formulation in each period, with the possible sequences 'AB' or 'BA' (where A = substrate and B = substrate & perpetrator). Equal allocation of subjects to each sequence will be ensured. The randomization will be balanced and the randomization schedule as well as the dispensing records will be kept in the drug store under controlled access. The study personnel involved in dispensing (pharmacist) and the Principal Investigator will be accountable for ensuring compliance to randomization schedule. Randomization schedule will be generated using SAS® software 9.3 or higher.

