#### **Recording of Adverse events**

All adverse events including both observed and volunteered ones will be recorded on the appropriate AE form (As per applicable Clinsync SOP), irrespective of its association with the investigational products. Laboratory parameters, which are outside the clinically acceptable ranges but are not clinically significant as per PI discretion, must be recorded in the lab report and respective CRF page as Nil Significant. Clinically significant abnormal laboratory values that represent a change from baseline should be recorded diagnostically as AE's (e.g.: for elevated serum glucose, the AE would be described diagnostically as "hyperglycemia"). Determination of Clinical significance is based on the Investigator's medical judgment/discretion. PI shall evaluate the event for its severity, causality and seriousness that require immediate report to IEC and sponsor.

The institutional ethics committee (IEC), regulatory agency (ies), and the sponsor will be informed regarding the adverse events as necessary. Any serious adverse events will be recorded in appropriate Serious Adverse Event Reporting Form (As per applicable Clinsync SOP).

The investigator shall report all serious and unexpected adverse events to the licensing authority, the sponsor or his representative, whosever had obtained permission from the licensing authority for the conduct of the study and the ethics committee that accorded approval to the study protocol, within twenty-four hours of their occurrence. In case the Investigator fails to report any serious adverse event within the stipulated period, he shall have to furnish the reason for the delay

Protocol for Drug-Drug Interaction Study of Spironolactone and Digoxin (Fasting Condition) Confidential

to the satisfaction of the Licensing Authority along with the report of the serious adverse event. The report of the serious adverse event, after due analysis shall be forwarded by the investigator to the Licensing Authority, chairman of the Ethics Committee and the Head of the Institution where the trial has been conducted within fourteen calendar days of the occurrence of the serious adverse event.

Serious adverse events report submitted to Licensing Authority will be in color coded binding, where the reports of SAEs of Deaths are submitted in red cover, the report of SAEs of injury other than deaths in blue cover and the remaining cases of SAE report in white cover.

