#### 15.1 Study Report and Documents

The final report format will be prepared as per ICH E3: Structure and Content of Clinical Study Reports and as per CDSCO regulatory requirements. Supplementary Documents such as screening records, Period I and Period II records etc. will be given along with study report. Frequency distributions of gender and race will be tabulated by treatment and sequence. Summary statistics for age, body weight, height, and Body Mass Index (BMI) will be tabulated by treatment sequence. Listings of pre study & post study laboratory values, listing of adverse event by subject, listing of urine drug scan by subject, listings of protocol deviations, summary of adverse events by organ class will be provided in clinical phase of CSR.

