#### Appendix II: Assessment schedule

The following time-and-events table illustrates the planned schedule of assessments:

\*Chest X-Ray (P/A view) will be taken for the volunteer whose X-Ray was taken more than 6 months

VASAV: INSTITUTIONAL Period I.

	MONTE CONTRACT OF TOTAL	1
Bernin I	ETHICS COMMITTEE	[
Pictures.		P_SP
2010	APProtocol-No.;ED	-011
ž	METRUVEL	

Protocol for Drug-Drug Interaction Study of Spironolactone and Digoxin (Fasting Condition) Confidential

\* ECG will be performed at 1.00 and 3.00 hours post dose in each period of the study and before check in of period-II & before checkout of each period.

\$ Spironolactone Oral Suspension will be administered from Day 1 to Day 5 and Day 7 to Day 9, to the subjects who will be randomized to treatment B as per randomization scheme and treatment A or B will be administered on day 6.

The day prior to drug administration in each period for this protocol will be considered as Day '-1'.

The day of dosing in each period for this protocol will be considered as Day 1.

-  Post study (hematology and biochemistry) laboratory evaluations will be done at last blood sample collection of the study.
-  Serum pregnancy test will be done for female subjects with child bearing potential and Urine pregnancy test will be done for post-menopausal female subjects during screening, each period check-in (Day '-1').
-  Evaluation of inclusion/exclusion criteria will be carried out prior to check-in of period I of the study.
-  Investigational products (substrate) will be dispensed a day before dosing and perpetrator will be dispensed on the day of dosing in each period of the study.

Condition)	Confidential

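### Laboratory data that allow a randomised comparison with and without spironolactone are only listed, while the report calls safety comparable on the absence of adverse events alone

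*Protocol*

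**What the plan says.** **What is measured.** The screening biochemistry panel (protocol section 11.2) includes sodium, potassium, chloride, calcium, magnesium, urea, creatinine and uric acid. Report section 12.4.2.1 states that the haematology and biochemistry "investigations done at screening were repeated at the end of the study". Appendix II, footnote 1, fixes the time: "laboratory evaluations will be done at last blood sample collection of the study". Separately, section 11.2 requires serum potassium and creatinine clearance on Day 5 of each period, to judge eligibility for Day 6 dosing.

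**What is done with it.** Protocol section 15.1 promises "Listings of pre study & post study laboratory values" and no laboratory summary or contrast. The SAP does not mention laboratory data. In the report, the entry under "Individual Subject Change" (12.4.2.2) is that it does not apply, and 12.4.2.3 points to a table of abnormal values.

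**What is concluded.** Monitoring safety is a secondary objective (protocol section 3.1). Under Safety Results, the report's synopsis goes from no recorded adverse events to comparable safety with and without spironolactone.

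**Allocation.** Section 4.2: "Equal allocation of subjects to each sequence will be ensured". Table 9 shows 14 subjects per sequence, all completing.

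**The concern.** The synopsis makes a comparative statement, but no laboratory comparison is planned or shown in the text. Protocol section 2.1.7 warns of hyperkalaemia and says that the suspension "can cause hyponatremia, hypomagnesemia, hypocalcemia, hypochloremic alkalosis"; it adds hyperuricaemia. Section 2.2.7 says that potassium or magnesium depletion makes the heart more sensitive to digoxin.

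A modest shift shared by the subjects on spironolactone, but inside the reference ranges, would not be flagged in an abnormal-value table. It would sit unsummarised in the listings. The samples that could estimate it were taken under randomisation, so what is missing is an analysis and not data. At stake is the laboratory support for the comparative safety statement.

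**Working it through.** **1. Group sizes.** Table 7 records 280 mL of suspension dosed per day in each period. At 20 mL per subject, 280/20 = 14 subjects on spironolactone per period, which agrees with Table 9. As a second check, 14 + 14 reproduces the report's intervals in Table 11. With SE = √ln(1+CV²) × √[0.5(1/14+1/14)] and t(0.95, 26) = 1.706:
- Cmax: SE = 0.3859 × 0.2673 = 0.1031; 64.597% × exp(±1.706 × 0.1031) = 54.18% to 77.02%, as stated.
- AUC0-96: SE = 0.1840 × 0.2673 = 0.0492; the result is 77.45% to 91.59%, as stated.

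**2. Treatment status at the end-of-study panel.** Section 9.4.1 dates the last spironolactone dose at 16 Apr 2019 (AB, Period II) and 19 Mar 2019 (BA, Period I). The last sample was on 17 Apr 2019.

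| | AB (n = 14) | BA (n = 14) |
|---|---|---|
| Days since last spironolactone dose | 1 | 29 |
| Metabolite half-lives elapsed (10–35 h, section 2.1.3) | 24/35 to 24/10 = 0.7 to 2.4 | at least 29 × 24/35 = 19.9 |
| Fraction of last canrenone exposure left | 2^(−24/10) to 2^(−24/35) = 0.19 to 0.62 | negligible |
| Time since Day 6 digoxin (13 Apr) | 96 h | 96 h |

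This is a concurrent randomised contrast between recent exposure and washout, with no dropout.

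**3. Treatment status on Day 5.** In each period the 14 subjects on Treatment B have had daily spironolactone since Day 1. That is four or five doses, because the time of the sample relative to the Day 5 dose is not stated. The 14 on Treatment A have had none in that period. Each subject appears once under each condition, before that period's digoxin dose.

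**4. Precision (90% CI half-width, in units of the analyte's between-subject SD).** The documents give no laboratory SD or correlation, so r is assumed at 0.3, 0.5 and 0.7.
- End of study, unadjusted: 1.706 × √(2/14) = 0.645 SD.
- End of study, adjusted for screening: 1.708 × √(2/14) × √(1−r²), with 25 df.
- Day 5 crossover: 1.706 × √(1−r) × √(2/28), with 26 df.

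| Assumed r | End of study, adjusted | Day 5 crossover |
|---|---|---|
| 0.3 | 0.62 | 0.38 |
| 0.5 | 0.56 | 0.32 |
| 0.7 | 0.46 | 0.25 |

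For potassium, with an assumed SD of 0.25–0.45 mmol/L and r = 0.5, the half-width is 0.14–0.25 mmol/L at end of study and 0.08–0.15 mmol/L on Day 5.

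**5. What the end-of-study contrast could detect.** At two-sided 5% and 80% power, the detectable difference is about 1.10 SD unadjusted and 0.95 SD adjusted at r = 0.5. It can yield an estimate but cannot exclude moderate effects.

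**The case against.** **The study's purpose is digoxin exposure, and its safety objective is only to monitor.** This stands in part: nothing here touches Cmax, AUC0-96 or the interaction conclusion. But the synopsis goes beyond monitoring to a statement of comparability, and that needs comparative evidence.

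**Imprecision.** With 14 per sequence and several analytes, wide intervals could reassure falsely or throw up chance signals. Screening and end-of-study samples are roughly 6 to 9 weeks apart, so r = 0.5 may be generous. This stands. It limits the tables to description, and a reader should not take them as enough to carry the safety conclusion alone.

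**Stronger readings that the documents do not support:**
- *The adverse-event rule is left without its input.* Section 11.3 says: "Clinically significant abnormal laboratory values that represent a change from baseline should be recorded diagnostically as AE's". A reader might infer that marking change as not applicable disables this rule. It does not: the investigator judges each subject's results, screening and end-of-study values both exist, and section 12.4.1 refers to individual listings in Appendix 16.2.8.
- *Spironolactone's listed electrolyte effects all raise digoxin risk.* Section 2.2.7 ties toxicity to low potassium, low magnesium and high calcium, and says that low calcium can cancel digoxin's effect. The effects listed for spironolactone include high potassium and low calcium. Among these three electrolytes, only low magnesium matches in direction.
- *A common shift would be visible nowhere.* Individual values are said to be in an appendix that is not in the reviewed text. The supportable statement is that no summary by sequence or treatment is planned or shown.
- *The end-of-study difference isolates spironolactone.* It compares Treatment B with Treatment A, and digoxin exposure was higher under B (Table 11). It is also one reading about 24 h after the last dose. The Day 5 contrast avoids the first limitation because it precedes that period's digoxin.

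**Conclusion.** The point holds as a gap in analysis and reporting. Only listings are planned, change is marked as not applicable, and safety is called comparable on the absence of adverse events alone. Meanwhile the collected data support a 28-subject within-subject contrast for potassium and creatinine clearance and a 14 v 14 randomised contrast for the rest of the panel.

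The group sizes and the end-of-study timing follow from the documents. The half-widths rest on assumed correlations, and the mmol/L figures also on an assumed potassium SD. Day 5 is clearly the better source for potassium and renal function. Sodium, chloride, calcium, magnesium, urea and uric acid rest on the end-of-study panel. The improvement is worth making because it is cheap, but it does not change the study's main result.

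**What to change.** - **Day 5.** Report the difference in serum potassium and creatinine clearance, with minus without spironolactone, from the crossover model (sequence, period, treatment, subject within sequence), with its 90% CI.
- **End of study.** Under 12.4.2.1, tabulate change from screening by sequence for each haematology and biochemistry parameter. For sodium, chloride, calcium, magnesium, urea and uric acid, give AB minus BA adjusted for the screening value, with its 90% CI. Show potassium and creatinine in the same way as support for Day 5.
- **Labels.** Mark the tables as descriptive, and as post hoc if they are added after study completion. Label the end-of-study contrast as about 24 h after the last spironolactone dose and 96 h after digoxin.
- **Use.** Cite the tables as supporting evidence for the comparative safety statement, not as its sole basis. State that a wide interval including zero does not show absence of effect. Limit any digoxin-toxicity rationale to the directions given in section 2.2.7.
- **SAP.** Add a sentence specifying these summaries.

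Cost: one or two tables from existing data and no new samples. The downside is the imprecision of the 14 v 14 estimates.

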#### 12.4.2.2 Individual Subject Change

Not applicable

## 12.4.2.3 Individual Clinically Significant Abnormalities

For individual clinically non significant abnormalities refer to Table 16 in section 14.3.4.

#### 12.5 VITAL SIGNS, PHYSICAL FINDINGS AND OTHER OBSERVATIONS RELATED TO SAFETY

Subjects were monitored for safety and tolerability during the entire study. The subject's Clinical examination along with vital signs (seated blood pressure, radial pulse rate and oral/aural temperature) were measured during check-in and check-out of each period.

Clinical examination was done on prior to dosing on Day 06 in each study period.

Oral/aural temperature was measured prior to dosing in each study period.

Protocol No. C-CMP-SPI-001

Confidential

Page 52 of 64

#### (Fasting Condition)

Confidential

Vital parameters – seated blood pressure and radial pulse rate were measured at prior to dosing, 1.00, 3.00, 5.00 and 11.00 hours post dose in each period from Day 1 to Day 5, and from Day 6 to Day 9, vitals were measured prior to dosing, at 1.00, 2.00, 3.00, 5.00, 8.00 and 11.00 hours post dose in each period.

Note

- On Day 6 the Vital signs (i.e. up to 3.00 hours post dose) was performed at bed side.
- From day 1 to Day 5, subjects who were randomized to treatment A, the vitals were checked at 5.00 hours post dose.

ECG was performed at 1.00 and 3.00 hours post dose in each period on Day 6, before period II check-in for subject study eligibility and at check-out of each period of the study. 2D echo was performed at the time of screening.

In each study period creatinine clearance and serum potassium levels were measured on Day 05 for the dosing eligibility of the subjects.

The screening clinical laboratory investigations included hematology, serum biochemistry, serology and urine analysis as detailed in the protocol. The hematology (except blood group and Rh typing) and biochemistry (except random blood sugar) investigations done at screening were repeated at the end of the study.

## **12.6 SAFETY CONCLUSIONS**

There were no adverse events reported in this study.

Space left blank intentionally.

(Fasting Condition)

Confidential

## 13. DISCUSSION AND OVERALL CONCLUSIONS

This was an open label, balanced, randomized, single-dose, two-treatment, twosequence, two-period, crossover, drug-drug interaction study in healthy adult human subjects under fasting condition.

This study was conducted in compliance with the final protocol, the applicable International Conference on Harmonization Guidelines for Good Clinical Practice (GCP), the relevant sections of Good Laboratory Practice (GLP), local laws and regulations (ICMR Guidelines on Biomedical Research, Schedule Y (amended version, 2014) of CDSCO (Central Drugs Standard Control Organization), relevant sections of Drugs and Cosmetics (First Amendment) Rules 2013, CDSCO Bioavailability & Bioequivalence guidelines, applicable USFDA guidelines, the provisions of Declaration of Helsinki (Brazil, October 2013) and applicable in-house SOP's.

The primary objective of this study was to characterize the pharmacokinetic profile of Digoxin (substrate drug) in the presence and absence of spironolactone (perpetrator) in healthy adult human subjects under fasting condition.

The secondary objective of this study was

- To assess whether there is a drug-drug interaction with concomitant use of spironolactone.
- To measure renal clearance (CLR)/Percent Recovered and unchanged drug excreted in urine (fe)/ Amount Recovered for digoxin in the presence and absence of spironolactone (perpetrator) in healthy adult human subjects under fasting condition
- To monitor safety of the subjects in drug-drug interaction study

The clinical part of the study was conducted in 28 subjects and the plasma samples and urine samples were sent to Bioanalytical department, ClinSync Clinical Research Pvt. Ltd., Hyderabad, where the bioanalysis was performed using validated LCMS/MS method. The details have been presented in a separate Bioanalytical Report. The pharmacokinetic parameters  $C_{max}$ , AUC0.96, and  $T_{max}$  for digoxin in plasma, Renal clearance (CLR) /Percent Recovered and Unchanged drug excreted in urine (fe)/Amount Recovered in urine were obtained using non-compartmental analysis (WinNonlin, version 8.1, Pharsight Corporation, USA). All statistical analyses were performed using SAS® version 9.3 (SAS Institute Inc., Cary, NC, USA).

Sampling was done up to 96.00 hours such that the plasma concentration and urine samples could be measured for adequately profiling the pharmacokinetics of the product and study periods were separated by a washout period of 28 days for

Confidential

complete elimination of the product substance. The pharmacokinetic and statistical analysis was done on all the 28 subjects.

The median time to reach peak plasma concentration  $(T_{max})$  for digoxin was 0.750 hr and 0.750 hr following administration of Treatment A and Treatment B respectively. The  $T_{max}$  ranged from 0.500 to 1.330 hr and 0.500 to 3.500 hr for Treatment A and Treatment B respectively.

The exposure ( $C_{max}$  and  $AUC_{0.96}$ ) of digoxin was not comparable for the Treatment A and Treatment B. The geometric mean  $C_{max}$  was 1456.085 and 2254.118 ng/mL for Treatment A and Treatment B respectively. The geometric mean  $AUC_{0.96}$  was 13473.043 and 15996.644 ng.hr/mL for Treatment A and Treatment B respectively.

The intra-subject variability of digoxin for  $C_{max}$  and AUC0.96 was 40.07% and 18.56% respectively.

Absence of drug-drug interaction would be established if the 90% confidence interval for the ratio of population geometric means between two treatments (A and B), based on log-transformed data, present in the equivalence limits of 80.00 - 125.00% for  $C_{max}$  and AUC0-96.

The % Treatment A / Treatment B ratio of digoxin was 64.597% and 84.224% for  $C_{max}$  and AUC0-96 respectively. The lower and the upper limits at 90% confidence interval were 54.18% - 77.02% and 77.45% - 91.59% for  $C_{max}$  and AUC0-96 respectively, which is not within the standard equivalence limit of 80.00-125.00%. Based on the above results presence of drug-drug interaction is established between digoxin and spironolactone.

By comparing  $C_{max}$  and  $AUC_{0.96}$  plasma values of Treatment A and Treatment B, we conclude that these values were increased by 35% and 16% respectively for Treatment B.

The Renal clearance (CLR)/Percent Recovered and unchanged drug excreted in urine (fe)/ Amount Recovered of digoxin was comparable for the Treatment A and Treatment B. The geometric mean Renal clearance (CLR)/Percent Recovered was 49.042 and 49.410 for Treatment A and Treatment B respectively. The geometric mean unchanged drug excreted in urine (fe)/ Amount Recovered was 122606.02 and 123523.87 for Treatment A and Treatment B respectively.

By comparing these values, we conclude that there is not much difference between Treatment A and Treatment B, with respect to Renal clearance (CLR)/Percent Recovered and unchanged drug excreted in urine (fe)/ Amount Recovered.

